## **6.6 Dose modification**

Dose modification is not applicable in this study.

## **6.7 Criteria for study hold or dosing stoppage**

UCB reserves the right to temporarily suspend or prematurely discontinue this study either at a single site, multiple sites, or at all sites at any time for reasons including, but not limited to, safety or ethical issues, inaccurate or incomplete data recording, noncompliance, or unsatisfactory enrollment with respect to quality or quantity. [REDACTED]

[REDACTED]

[REDACTED]

If the study is prematurely terminated or suspended, UCB (or its representative) will inform the Investigators/institutions and the regulatory authority(ies) of the termination or suspension and the reason(s) for the termination or suspension, in accordance with applicable regulatory requirement(s). The Institutional Review Board (IRB)/ Independent Ethics Committee (IEC) should also be informed and provided with reason(s) for the termination or suspension by the Sponsor or by the Investigator/institution, as specified by the applicable regulatory requirement(s). In addition, arrangements will be made for the return or destruction of all unused IMP and other material in accordance with UCB procedures for the study.

Detailed procedures for reporting SAEs and other safety events which may meet study hold criteria are provided in Appendix 8.

## **6.8 Treatment after the end of the study**

Study participants who complete HS0003 will have the option of enrolling in a Phase 3, multicenter, extension study (HS0005).

Study participants who elect not to enroll in HS0005 at Week 48 will be scheduled to have the SFU Visit 20 weeks after the final injection of IMP. During the SFU, if study participants' HS deteriorates, the Investigator may consider standard of care for HS treatment after discussion with the Medical Monitor or UCB study physician. Note that the half-life of bimekizumab must be considered in selection of appropriate HS treatments during the SFU period. All concomitant

medications and HS interventions administered during the SFU will be recorded on the appropriate eCRF pages.

## **7 DISCONTINUATION OF STUDY MEDICATION AND PARTICIPANT DISCONTINUATION/WITHDRAWAL**

### **7.1 Discontinuation of study medication**

Study medication will be stopped if the study participant develops a medical condition, adverse event (AE), or laboratory abnormality that, in the opinion of the Investigator, compromises the safety of the study participant or his or her ability to continue participation in the study. Study participants who are discontinued from IMP should be encouraged by the Investigator to return for all scheduled visits through Week 48, and the SFU Visit (if the Week 48 Visit is  $\geq 20$  weeks after the final dose of IMP, the SFU Visit is not required). Any study participant who discontinues IMP but continues in the study should be discussed with the Medical Monitor or UCB study physician.

In all cases the study participant should be followed until the condition has resolved as agreed by the Investigator and the UCB study physician. Investigators should contact the Medical Monitor and/or UCB study physician, in advance whenever possible, to discuss the withdrawal of a study participant.

Study medication will be stopped if the study participant has a confirmed positive coronavirus disease 2019 (COVID-19) test result or a suspected COVID-19 infection. Study medication can be resumed after the participant's recovery from COVID-19, based on the Investigator's clinical judgement. All such cases must be discussed with the Medical Monitor or UCB study physician.

#### **7.1.1 Study participant does not achieve partial response**

If a study participant does not achieve a partial response (defined as a  $\geq 25\%$  reduction in AN count from Baseline [Week 0]) at any visit from Week 32 to 46, the Investigator should contact the Medical Monitor to discuss whether the study participant should continue on study.

#### **7.1.2 Potential drug-induced liver injury IMP discontinuation criteria**

Study participants with potential drug-induced liver injury (PDILI) must be assessed to determine if IMP must be discontinued. In addition, all concomitant medications and herbal supplements that are not medically necessary should also be discontinued.

##### **7.1.2.1 PDILI Discontinuation Criteria**

The PDILI criteria below require immediate discontinuation of IMP for study participants with either of the following (see Section 10.6.2.1):

- ALT or AST  $\geq 8 \times \text{ULN}$
- ALT or AST  $\geq 3 \times \text{ULN}$  and coexisting total bilirubin  $\geq 2 \times \text{ULN}$

Similarly, the PDILI criterion below requires immediate discontinuation of IMP for:

- Study participants with ALT or AST  $\geq 3 \times \text{ULN}$  who exhibit temporally associated symptoms of hepatitis or hypersensitivity. Hepatitis symptoms include fatigue, nausea, vomiting, right

upper quadrant pain or tenderness. Hypersensitivity symptoms include fever (without clear alternative cause), rash, or eosinophilia (ie, >5%).

If a nondrug-related cause for the symptoms can be confirmed, these study participants may resume IMP administration after discussion with the Medical Monitor and/or UCB study physician, but only when the requirements for rechallenge with IMP as provided in Section 10.6.2.1 are followed.

The PDILI criterion below allows for study participants to continue on IMP at the discretion of the Investigator.

- Study participants with ALT or AST  $\geq 5 \times \text{ULN}$  and  $< 8 \times \text{ULN}$ , total bilirubin  $< 2 \times \text{ULN}$ , and no eosinophilia (ie,  $\leq 5\%$ ), with no fever, rash, or symptoms of hepatitis (eg, fatigue, nausea, vomiting, right upper quadrant pain or tenderness).

Evaluation of PDILI must be initiated as described in Section 10.6 (Appendix 6) with repeat tests performed in 2 weeks. Upon retest, if ALT or AST values have reduced to  $< 5 \times \text{ULN}$ , the study participant can continue with the study. However, if ALT or AST remains  $\geq 5 \times \text{ULN}$  and  $< 8 \times \text{ULN}$  after retest, IMP should be temporarily withheld and study participant should undergo a repeat test in 2 weeks. If ALT or AST values remain  $\geq 5 \times \text{ULN}$  even after the second retest, then the study participant should be permanently withdrawn from IMP and should be followed for possible PDILI.

If study participants are unable to comply with the applicable monitoring schedule, IMP must be discontinued immediately.

Investigators should attempt to obtain information on study participants in the case of IMP discontinuation to complete the final evaluation. Study participants with PDILI should not be withdrawn from the study until investigation and monitoring are complete. All results of these evaluations and observations, as well as the reason(s) for IMP discontinuation and study participant withdrawal (if applicable), must be recorded in the source documents. The eCRF must document the primary reason for IMP discontinuation.

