**Table 10-1: Required investigations and follow-up for PDILI**

Laboratory value		Symptoms a of hepatitis or hypersensitivity	Immediate		Follow up	
ALT or AST	Total bilirubin		Consultation requirements	Actions	Testing	Evaluation
$\geq 5\times\text{ULN}$ (and $\geq 2\times$ Baseline) and $<8\times\text{ULN}$	$<2\times\text{ULN}$	No	
Discussion with Medical Monitor required.
 
Consider need for hepatology consult if there is no evidence of resolution (see Follow-up requirements).c
	
Further investigation – immediate IMP discontinuation not required (see Section 10.6.2).
 
IMP discontinuation required if any of the following occur:
 
 
• Subject cannot comply with monitoring schedule.
 
• Liver chemistry values continue to increase
 
• Liver chemistry values remain <math>\geq 5\times\text{ULN}</math> (and <math>\geq 2\times</math> baseline) after 4 weeks of monitoring without evidence of resolution
 
	
Essential: Every attempt must be made to have repeat liver chemistry values and additional testing completed within 48 hours at the site with HCP (see Section 10.6.3).
	
Monitoring of liver chemistry values at least twice per week for 2 weeks.e
 
 
• Immediate IMP discontinuation required if liver chemistry values continue to increase.
 
 
After 2 weeks of monitoring liver chemistry values:
 
 
• ALT or AST remains <math>\geq 5\times\text{ULN}</math> <math><8\times\text{ULN}</math>, IMP should be temporarily withheld and subject should undergo repeat test in 2 weeks.
 
 
Continue IMP if ALT or AST values <math><5\times\text{ULN}</math>; continue to monitor at least twice per week until values normalize, stabilize, or return to within baseline values.
 
If ALT or AST remains <math>\geq 5\times\text{ULN}</math> after second retest, immediate IMP discontinuation required.
 
Continue to monitor until values normalize, stabilize, or return to within baseline values.d

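### For asymptomatic ALT/AST of at least 5 and below 8 times ULN, Section 7.1.2.1 and Table 10-1 give different conditions for stopping IMP and should be reconciled

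*Protocol*

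**What the plan says.** Section 7.1.2.1 of the Protocol (PDILI Discontinuation Criteria) first lists findings that call for immediate discontinuation: ALT or AST at or above 8 times ULN, and ALT or AST at or above 3 times ULN with raised bilirubin or with symptoms. It then turns to the band from 5 to below 8 times ULN with bilirubin below 2 times ULN and no symptoms: "The PDILI criterion below allows for study participants to continue on IMP at the discretion of the Investigator". For this band it sends evaluation to Section 10.6 (Appendix 6), "with repeat tests performed in 2 weeks". A retest below 5 times ULN lets the participant continue. If the retest is still in the band, "IMP should be temporarily withheld and study participant should undergo a repeat test in 2 weeks". If values are still at or above 5 times ULN at that second retest, withdrawal from IMP is permanent. The section closes with: "If study participants are unable to comply with the applicable monitoring schedule, IMP must be discontinued immediately".

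Table 10-1 in Appendix 6 has a row for the same band, limited to values that are also at least 2 times Baseline. On the first repeat test it says: "Every attempt must be made to have repeat liver chemistry values and additional testing completed within 48 hours". On what follows it says: "Monitoring of liver chemistry values at least twice per week for 2 weeks", and then: "Immediate IMP discontinuation required if liver chemistry values continue to increase". After the 2 weeks it gives continue, withhold and discontinue steps like those in Section 7.1.2.1.

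Section 7.1.2.1.1 refers to Table 10-1 for follow-up monitoring of PDILI events. Footnote e of the table allows the Investigator and the sponsor's physician to agree another monitoring schedule.

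**The concern.** A site with a participant in this band has two texts to follow, and they do not give the same stopping conditions. The rule that stops IMP on rising values appears only in the appendix table. The section that carries the title of discontinuation criteria offers nothing between continuing and temporary withholding until the second retest.

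The difference has consequences for the participant. Appendix 6 treats IMP stopped for PDILI as permanently stopped unless another diagnosis fully explains the findings, and Section 10.6.2.1 allows rechallenge only if every item on a list is met. Neither text attaches those conditions to temporary withholding. Hepatic events and PDILI are a prespecified safety topic (Section 8.3.7), so sites should act on one rule.

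**Working it through.** No sample size, power or error rate is involved. The check sets the two texts side by side, with one short piece of arithmetic for the Baseline condition.

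**1. Side by side, ALT/AST at least 5 and below 8 times ULN, bilirubin below 2 times ULN, no symptoms**

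| Item | Section 7.1.2.1 | Table 10-1 |
|---|---|---|
| Further entry condition | none | value at least 2 times Baseline |
| First repeat test | 2 weeks, with evaluation under Appendix 6 | every attempt within 48 hours |
| Tests in the first 2 weeks | none stated beyond the retest | at least twice per week, or as agreed (footnote e) |
| Values keep rising but stay below 8 times ULN | no rule | immediate discontinuation |
| Still in the band at 2 weeks | withhold, retest 2 weeks later | withhold, retest 2 weeks later |
| Still at or above 5 times ULN at the second retest (about 4 weeks) | permanent withdrawal from IMP | discontinuation |

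The last two rows place their decisions at the same times. The first four differ.

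**2. The rise trigger.** Take assumed values: ALT 5.2 times ULN on the initial test and 7.0 times ULN on repeat, no symptoms, bilirubin below 2 times ULN, Baseline normal. Under Section 7.1.2.1 the value is still in the band at the 2-week retest, so IMP is withheld temporarily. Under Table 10-1, if the rise counts as a continued increase, IMP is discontinued at once. One course of values gives two actions.

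**3. Which text governs stopping.** Section 7.2, item 5a, cites Section 7.1.2 for hepatotoxicity. The opening of Appendix 6 sends the question of whether IMP must be discontinued back to Section 7.1.2, and its paragraph on permanent discontinuation cites Section 7.1.2.1. Section 10.6.2 cites Section 7.1.2 and Table 10-1 together. A reader who follows these references therefore meets both rules, with no statement of which prevails.

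**4. The Baseline condition.** Let B be Baseline and x the new value, both in multiples of ULN. Section 7.1.2.1 applies when 5 ≤ x < 8. The table row also needs x ≥ 2B. A value meets the first but not the second when 5 ≤ x < 2B, which is possible only if 2B > 5, that is B > 2.5. Exclusion criterion 29 bars ALT or AST at or above 3 times ULN at Screening. If Baseline is also below 3, then 2B < 6, and the gap is limited to B between 2.5 and 3 with x between 5 and 6. With an assumed B = 2.8, 2B = 5.6, so an asymptomatic value of 5.2 with bilirubin below 2 times ULN falls under Section 7.1.2.1 but in no row of Table 10-1. The exclusion limit is set at Screening only, so a higher value at the Baseline Visit would widen the gap.

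**5. The retest phrase.** The 2 weeks in Section 7.1.2.1 may mean the decision test that the table also places after 2 weeks of monitoring, or it may mean the first repeat test. The sentence does not say which. The closing rule on participants who cannot comply refers to an applicable schedule, so the phrase needs to be clear.

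**The case against.** The strongest reply is that the two texts were meant to be read together. The sentence with the 2-week retest itself sends evaluation to Section 10.6, and Section 7.1.2.1.1, directly below, adopts Table 10-1 for follow-up monitoring. The 2-week and 4-week decision points match, so the 2-week retest can be read as the decision test, with the table supplying the tests in between. The 48-hour test is worded as an effort to be made, and footnote e lets the twice-weekly schedule be changed by agreement. The Baseline gap is narrow. A rise to 8 times ULN or above, bilirubin at or above 2 times ULN, or symptoms lead to immediate discontinuation in both texts.

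Most of this stands, and it disposes of a broader reading. A reader might infer that the whole monitoring schedule depends on which page a site opens, with one retest in the first 2 weeks under the main text against at least four under the table. The documents do not support that contrast, because it requires ignoring Section 7.1.2.1.1.

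The reply does not reach the stopping rule. Section 7.1.2.1.1 adopts the table for monitoring and does not clearly import its trigger for discontinuation. Footnote e is attached to the schedule and not to the stop on rising values. For participants in the Baseline gap, the reference to the table leads to no matching row.

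**Conclusion.** The conflict is real and narrow. The two texts give different conditions for stopping IMP in the same band: immediate discontinuation on continued increase appears only in Table 10-1, and Section 7.1.2.1 reaches only temporary withholding at the first retest. The entry range also differs, for Baseline values above 2.5 times ULN, and the 2-week retest phrase is ambiguous.

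The documents give no count of participants expected in this band; the number is likely small. The conclusion rests on the wording alone. The ALT values and the Baseline of 2.8 times ULN are assumed illustrations.

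A reader might also infer an effect on the primary endpoint, since Section 9.3.1 counts discontinuation for an adverse event before Week 16 as non-response. That would need an asymptomatic participant in the band before Week 16, rising but below 8 times ULN, handled under one text and not the other. Nothing in the documents suggests this would be frequent enough to matter for HiSCR50, so the point is about participant safety and consistent conduct. No view is taken on which rule is right.

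**What to change.** Reconcile Section 7.1.2.1 and Table 10-1 so that both state the same trigger range (with or without the Baseline condition), the same timing for the first and later retests, and the same conditions for withholding or stopping IMP. The wording should make clear whether the 2-week test is the first repeat or the decision test, and whether continued increase below 8 times ULN is a stopping criterion. The sponsor decides which text stands.

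The cost is wording in the next amendment or a clarification letter to sites. No analysis, sample size or data collection form need change on account of this point.

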#### 7.1.2.1.1 Follow-up evaluation

Potential drug-induced liver injury events require follow-up monitoring as described in Table 10-1. Monitoring should continue until liver chemistry values normalize, stabilize, or return to Baseline. Determination of stabilization is at the discretion of the Investigator in consultation with the hepatologist (as applicable) and UCB study physician, as needed.

#### 7.1.3 Treatment interruptions

If a study participant is found to be persistently noncompliant (for example, missing 2 or more of the doses in the Initial Treatment Period or 3 or more doses during Maintenance Treatment Period) the Sponsor, in conjunction with the Investigator, will make a decision as to whether the study participant should be withdrawn from the study.

Note: Doses of IMP that were missed due to a reasonable interfering AE that does not allow administration of IMP due to safety reasons will not be considered for the evaluation of study participant discontinuation. Evaluation of the reasonability of the AE should be discussed immediately with the Medical Monitor.

Any participant who develops a clinically important infection or recurrent infections not responsive to standard therapy during the study must discontinue IMP until resolution of the infection. The Investigator should use clinical judgement in deciding whether the participant should restart IMP and contact the Medical Monitor and UCB study physician to confirm the participant's suitability for continued participation in the study.

## 7.2 Participant discontinuation/withdrawal from the study

Note: For female study participants, please see Section 8.3.5 for pregnancy that occurs during the study as evidenced by a positive pregnancy test.

Study participants are free to withdraw from the study at any time, without prejudice to their continued care.

A study participant may withdraw from the study at any time at his or her own request, or may be withdrawn at any time at the discretion of the Investigator for safety, behavioral, compliance, or administrative reasons.

If the study participant withdraws consent for disclosure of future information, the Sponsor may retain and continue to use any data collected before such a withdrawal of consent.

If a study participant withdraws from the study, he or she may request destruction of any samples taken and not tested, and the Investigator must document this in the site study records.

See the Schedule of Activities (Table 1-1) for data to be collected at the time of study discontinuation and follow-up and for any further evaluations that need to be completed.

If a study participant does not achieve a partial response (defined as a  $\geq 25\%$  reduction in AN count from Baseline [Week 0]) at any visit from Week 32 to 46, the Investigator should contact the Medical Monitor to discuss whether the study participant should continue on study.

Study participants will be withdrawn from the study, after being encouraged to complete the Premature End of Treatment (PEOT) and the SFU Visit if either of the following events occur:

1. Study participant withdraws his or her consent.
2. The Sponsor or a regulatory agency requests withdrawal of the study participant.

Study participants should be withdrawn from IMP and encouraged by the Investigator to return for all scheduled visits through Week 48, and the SFU Visit (if the Week 48 Visit is  $\geq 20$  weeks after the final dose of IMP, the SFU Visit is not required) if any of the following events occur:

1. Study participant develops an illness that would interfere with his or her continued participation.
2. Study participant is noncompliant with the study procedures or medications in the opinion of the Investigator.
3. Study participant takes prohibited concomitant medications as defined in this protocol (Section 6.5.2) that may present a risk to the safety of the participant or the integrity of the study data, in the opinion of the Investigator and/or the Medical Monitor and/or UCB study physician.

4. Study participant requires more than the number of protocol-allowed lesion interventions (see Section 6.5.3.2).
5. Study participant has a clinical laboratory value meeting any of the following criteria:
  - a. Hepatotoxicity as described in Section 7.1.2.
  - b. A laboratory value meeting any of the following criteria:
    - Absolute neutrophil count  $<1.0 \times 10^3/\mu\text{L}$
    - Absolute lymphocyte count  $<200 \text{ cells}/\mu\text{L}$

Study participants may remain on IMP if the result is transient. A retest is required within 1 to 2 weeks at a scheduled or unscheduled visit. If the repeat absolute neutrophil count or absolute lymphocyte count is still below the allowable values, the participant must be discontinued from the IMP. If the repeat absolute neutrophil count or absolute lymphocyte count is above the allowable values, the participant may continue to receive IMP.

6. There is confirmation of a pregnancy during the study, as evidenced by a positive pregnancy test (see Section 8.3.5 for more information regarding pregnancies).
7. A study participant considered as having either a suspected new LTBI or who develops active TB or an NTM infection during the study (including but not limited to, conversion demonstrated by interferon gamma release assay [IGRA] or other diagnostic means) must be immediately discontinued from IMP.
  - The study participant must immediately be permanently withdrawn from the study if further examinations result in a diagnosis of the following:
    - active TB or
    - an NTM infection, or
    - latent TB infection and study participant does not initiate TB prophylactic therapy, prematurely discontinues TB prophylactic therapy, or, in the opinion of the Investigator or Sponsor, is noncompliant with TB prophylactic therapy.

The PEOT Visit must be scheduled as soon as possible, but not later than the next regular visit.

- If the study participant is diagnosed with LTBI during the study and desires to continue in the study, he or she must immediately discontinue IMP and start TB prophylactic therapy. After at least 4 weeks of TB prophylaxis, the IMP can be restarted after discussion with the UCB study physician regarding results of laboratory assessments, physical examination, and TB questionnaire. The full course of TB prophylaxis treatment will be completed during the study.

Confirmed active TB is an SAE and must be captured on an SAE Report Form and provided to the Sponsor in accordance with SAE reporting requirements. As with all SAEs, periodic follow-up reports should be completed as per protocol requirements until such time as the TB infection resolves.

Additional information on TB policies is provided in Section 8.2.6.

8. Study participants with newly diagnosed IBD or with IBD flares during the study must:

- Be referred, as appropriate, to a healthcare professional treating IBD, such as a gastroenterologist
- Discontinue IMP and be followed-up until resolution of active IBD symptoms

If IBD flares increase in severity or frequency during the study, the Investigator should use clinical judgement in deciding whether the study participant should continue on IMP and contact the Medical Monitor and UCB study physician to confirm the study participant's suitability for continued participation in the study.

9. Study participants must be referred immediately to a mental healthcare professional and may be withdrawn from the study based upon the Investigator's judgment of benefit/risk for:

- Active suicidal ideation as indicated by a positive response ("Yes") to Question 4 of the "Since Last Visit" version of the eC-SSRS
- Moderately severe major depression as indicated by a PHQ-9 score of 15 to 19 if this represents an increase of at least 3 points compared to the last visit

The mental health consultation must be recorded in the study participant's source documentation.

10. Study participants must be referred immediately to a mental healthcare professional and must be withdrawn from the study in case of:

- Active suicidal ideation as indicated by a positive response ("Yes") to Question 5 of the "Since Last Visit" version of the eC-SSRS.
- Any suicidal behavior since last visit.
- Severe major depression as indicated by a PHQ-9 score  $\geq 20$ .

The mental health consultation must be recorded in the study participant's source documentation.

Investigators should contact the Medical Monitor in advance, whenever possible, to discuss the withdrawal of a study participant from IMP or from the study.

Study participants withdrawing from the study who are not continuing for all scheduled visits through Week 48, will undergo the PEOT Visit and the SFU Visit 20 weeks after their final dose of IMP, as applicable.

The eCRF must document the primary reason for withdrawal or discontinuation.

Investigators should contact the Medical Monitor and/or UCB study physician, whenever possible, to discuss the withdrawal of a study participant in advance.

Withdrawn participants will not be replaced.

